8.3 Clinical Laboratory Evaluations

All derivations, analyses and summaries are not applicable (details in Section 1 and Section 5.3).

Laboratory evaluations will be conducted at screening and during treatment period, as described in protocol and Section 14.3. For hematology and clinical chemistry variables, change from baseline will be calculated for each post-baseline visit, and the laboratory values will be evaluated according to the NCI CTCAE version 4.03 toxicity grading scale by the investigator. All the laboratory data will be analyzed for the SAF set.

Observed laboratory values will be compared to the reference range and classified as low (below range), normal (within range or on limits of range) and high (above range).

The maximum (or minimum) value during treatment will be defined for each laboratory parameter as the maximum (or minimum) post-baseline value at any time.

Summaries of laboratory results will be provided in standard international units.

For continuous laboratory assessments observed values and changes from baseline will be summarized using descriptive statistics at each visit.

Shift tables relative to the CTC grade will be produced to summarize the change from baseline to the worst CTC grade during treatment period. For specific parameters separate shift tables indicating hyper- and hypo- directionality of change will be produced. The following laboratory parameters will be included in the shift tables:

- Haematology: hemoglobin, lymphocyte absolute counts, neutrophil absolute counts, platelet counts, leukocytes
- Clinical chemistry: albumin, alanine aminotransferase (ALT), aspartate aminotransferase (AST), alkaline phosphatase (ALP), total bilirubin, creatinine, corrected calcium (increased and decreased), glucose (increased and decreased), potassium (increased and decreased), magnesium (increased and decreased), sodium (increased and decreased)

For the laboratory parameters with no CTCAE grading, shifts tables from baseline to minimum and maximum value during treatment will be created.

For urinalysis variables, a table will summarize the shift in the absence/presence of protein, glucose, blood, ketones, bilirubin, urobilinogen, nitrate, leukocyte esterase, red blood cells, white blood cells, bacteria, and casts from baseline to each scheduled visit during treatment.

All laboratory test results (including urinalysis) will be presented in subject data listings.

8.4 Vital Signs

All derivations, analyses and summaries are not applicable (details in Section 1 and Section 5.3).

For vital signs, systolic and diastolic blood pressure (supine and standing), heart rate (supine and standing), weight, and respiratory rate and changes in these parameters from baseline will be summarized at each scheduled measurement using descriptive statistics. The summary table will be produced for the SAF set. All vital sign data will be included in a subject data listing.

8.5 Recurrent Malignancies

All derivations, analyses and summaries are not applicable (details in Section 1 and Section 5.3).

Recurrent malignancy will be assessed at screening and all visits during the study. The time to recurrent malignancies will be defined as the time interval from the first dose date of study treatment to the first onset date of recurrent malignancies. Subject without any recurrent malignancies will be censored on the last follow-up date. Subject who have died without recurrent malignancies will be censored on the date of death, and this censoring will be handled separately in the estimation. The competing risk method will be used to estimate the cumulative incidence of recurrent malignancies at Days 180 and 365.

The incidence of recurrent malignancies will also be summarized by the number and percentage of subjects who had at least one presence of recurrent malignancy by Days 180 and 365 for the SAF set.

8.6 Infection

All derivations, analyses and summaries are not applicable (details in Section 1 and Section 5.3).

The infections and the type of infections will be identified using preferred terms of AEs by the medical team. The incidence of infection will be analyzed as a time to event outcome measure. The time to infection will be defined as the time interval from the first dose date of study treatment to the first onset date of infection. Subject without any infection or the infection of interest or death will be censored on the last follow-up date. Subject who have died without any infection will be censored on the date of death, and this censoring will be handled separately in the estimation. The competing risk method will be used to estimate the cumulative incidence function of infection at Days 28, 56, 180, and 365 for any infection and by the type of infections, including viral infection, bacterial infection, and fungal infection.

The number and percentage of subjects with infection for at least once by Days 28, 56, 180 and 365 will be summarized for any infection and by the type of infections.

9. EVALUATION OF PHARMACOKINETICS

9.1 Concentration data

Subjects with partial data will be evaluated on a case-by-case basis to determine if sufficient data are available for reliable estimation of PK parameters.

A listing of PK blood sample collection times as well as derived sampling time deviations and PK concentration data will be provided. A listing of PK stool sample collection times, sample weights and concentration and amount data will be provided where available.

Due to study discontinuation no population PK analysis is planned to be conducted based on the concentration data collected in this study.

9.2 Pharmacokinetic parameters

A listing of PK parameters by Day (Days 1, 13, and 22) will be provided.

For PK parameter calculations, predose samples that are BLQ or missing will be assigned a numerical value of zero. Any other BLQ concentrations will be assigned a value of zero if they precede quantifiable samples in the initial portion of the profile. A BLQ

value that occurs between quantifiable data points, especially prior to C_{max} , will be evaluated to determine if an assigned concentration of zero makes sense, or if exclusion of the data is warranted. Following C_{max} , BLQ values embedded between 2 quantifiable data points will be treated as missing when calculating PK parameters. If a BLQ value occurs at the end of the collection interval (after the last quantifiable concentration), it will be set to zero. If consecutive BLQ concentrations are followed by quantifiable concentrations in the terminal portion of the concentration curve, these quantified values will be excluded from the PK analysis by setting them to missing, unless otherwise warranted by the concentration-time profile.

Blood samples for PK collected after the infusion on Day 1, Day 13 or Day 22 prior to the next infusion will be used to estimate the following PK parameters if possible. A minimum of 3 quantifiable concentration-time data points will be required for calculation of PK parameters. The following PK parameters will be estimated for GLASSIA in plasma by non-compartmental methods using actual elapsed time from dosing, with additional parameters determined as appropriate.

$AUC_{(0-inf)}$	Area under the concentration-time curve in the sampled matrix from zero (predose) extrapolated to infinite time, calculated by linear up/log down trapezoidal summation and extrapolated to infinity by addition of the last quantifiable concentration divided by the elimination rate constant: $AUC_{(0-last)} + C_{last}/\lambda_z$.
$AUC(0-t)$	Area under the concentration-time curve in the sampled matrix from zero (predose) until time "t", calculated by linear up/log down trapezoidal summation.
C_{max}	Maximum concentration in plasma, obtained directly from the observed concentration versus time data.
t_{max}	Time of maximum concentration (h), obtained directly from the observed concentration versus time data.
λ_z	Apparent terminal rate constant (1/h), determined by linear regression of the terminal points of the log-linear concentration-time curve. Visual assessment will be used to identify the terminal linear phase of the concentration-time profile. A minimum of 3 data points will be used for determination.
$t_{1/2}$	Apparent terminal half-life (h), determined as $\ln 2/\lambda_z$.
CL	Systemic clearance after intravenous dosing (L/h), calculated as dose divided by $AUC(0-inf)$.
V_{ss}	Volume of distribution at steady state following intravenous dosing (L), calculated as mean residence time (MRT) extrapolated to infinity multiplied by clearance ($MRT_{inf} * CL$)
MRT	Mean residence time

The following PK parameters will be calculated for diagnostic purposes and listed, but will not be summarized.

$t_{1/2}$, Interval	The time interval (h) of the log-linear regression to determine λ_z .
$t_{1/2}$, N	Number of data points included in the log-linear regression analysis to determine λ_z . A minimum of 3 data points will be used for determination.
Rsq	Goodness of fit statistic for calculation of λ_z (Regression coefficient/coefficient of determination).
$\%AUC_{ex}$	Percentage of $AUC_{(0-inf)}$ obtained by extrapolation, calculated as $[(C_{last}/\lambda_z)/AUC_{(0-inf)}] \times 100$.

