Continued on next page

Continued

- ^e Coagulation panel includes PT, PTT and INR.
- ^f Urinalysis assessments include: color, specific gravity, pH, protein, glucose, ketones, bilirubin, urobilinogen, blood, nitrate, leukocyte esterase and microscopic examination (RBC, WBC, bacteria and casts).
- ^g For the determination of stool A₁PI level and clearance and calprotectin concentrations. One sample will be collected either during screening or prior to the first study treatment administration on Day 0. On Days 0 and 12, a sample will be collected during the 24 hours after the start of study treatment infusion. On Day 28, the sample will be collected prior to the start of study treatment infusion.
- ^h If study treatment is administered peripherally, the PK samples should be taken from the opposite arm as the study treatment administration, if possible. If study treatment is administered via a central indwelling catheter, the PK samples may be taken from the same infusion line, if the infusion line is flushed prior to collection of the PK sample and the first 3 mL of blood is discarded.
The PK samples for the measurement of plasma A₁PI levels will be collected at the following timepoints:
 - Part 1, Cohort 1
 - Day 0: Prior to start of study treatment infusion, at 15 (±5) minutes, 2 hours (±12 minutes), 4 hours (±24 minutes), 8 hours (±48 minutes), 12 hours (±72 minutes) and 24 hours (±144 minutes) (ie, Day 1) following the end of study treatment infusion
 - Day 2: Within 2 hours prior to start of study treatment infusion, and at 15 (±5) minutes following the end of study treatment infusion
 - Day 12: Within 2 hours prior to start of study treatment infusion, at 15 (±5) minutes, 2 hours (±12 minutes), 4 hours (±24 minutes), 8 hours (±48 minutes), 12 hours (±72 minutes) and 24 hours (±144 minutes) (ie, Day 13) following the end of study treatment infusion
 - Day 14: Within 2 hours prior to start of study treatment infusion, and at 15 (±5) minutes following the end of study treatment infusion
 - Day 21: Within 2 hours prior to start of study treatment infusion, and at 15 (±5) minutes following the end of study treatment infusion
 - Day 28: During the Day 28 clinic visit, but must be prior to the next study treatment

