 - Day 49: Within 2 hours prior to start of study treatment, at 15 (±5) minutes, 2 hours (±12 minutes), 4 hours (±24 minutes), 24 hours (±144 minutes) (ie, Day 50), 72 (±7) hours (ie, Day 52) and 120 (±12) hours (ie, Day 54) following the end of study treatment infusion
 - Day 56: During the Day 56 clinic visit
 - Part 2
 - Day 0: Prior to start of study treatment infusion, and at 15 (±5) minutes following the end of study treatment infusion
 - Day 2: Within 2 hours prior to study treatment infusion
 - Day 12: Within 2 hours prior to start of study treatment infusion, and at 15 (±5) minutes following the end of study treatment infusion
 - Day 14: Within 2 hours prior to study treatment infusion
 - Day 21: Within 2 hours prior to start of study treatment infusion, and at 15 (±5) minutes following the end of study treatment infusion
 - Day 28: During the Day 28 clinic visit, but must be prior to the next study treatment infusion.
 - Day 49: Within 2 hours prior to start of study treatment infusion, and at 15 (±5) minutes following the end of study treatment infusion
 - Day 56: During the Day 56 clinic visit
- ⁱ Biomarkers to be assessed in Parts 1 and 2 will include cytokines IL-2, IL-6, IL-8, and IL-10; IL-1RA and T cell subpopulations, including CD4⁺ CD25⁺ CD127⁺ FoxP3⁺ Tregs; in Part 2 only, the following biomarkers will also be assessed: Reg3α, ST2, and TNFR1.
- ^j Antibody or nucleic acid test. The results of an HIV test performed within the 3 months prior to screening may be used instead.

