 - Day 22: Within 2 hours prior to start of study treatment infusion, at 15 (±5) minutes, 2 hours (±12 minutes), 4 hours (±24 minutes), 24 hours (±144 minutes) (ie, Day 23), 72 (±7) hours (ie, Day 25) and 120 (±12) hours (ie, Day 27) following the end of study treatment infusion
 - Day 28: During the Day 28 clinic visit, but must be prior to the next study treatment
 - Day 50: Within 2 hours prior to start of study treatment, at 15 (±5) minutes, 2 hours (±12 minutes), 4 hours (±24 minutes), 24 hours (±144 minutes) (ie, Day 51), 72 (±7) hours (ie, Day 53) and 120 (±12) hours (ie, Day 55) following the end of study treatment infusion
 - Day 56: During the Day 56 clinic visit
- ^j Biomarkers will include cytokines IL-2, IL-6, IL-8, IL-10 and IL-32; heparan sulfate; Reg3α; ST2; TNFR1; IL-1RA and T cell subpopulations, including CD4⁺ CD25⁺ CD127⁺ FoxP3⁺ Tregs.
- ^k Antibody or nucleic acid test. The results of an HIV test performed within the 3 months prior to screening may be used instead.

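### SAP 9.2 divides dose by AUC to infinity on repeat-dose days, which understates clearance, and plans no parameters for the full Day 50 profile

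*SAP*

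**What the plan says.** SAP 9.2 restricts the non-compartmental analysis to three days in two separate sentences. One sets the output: "A listing of PK parameters by Day (Days 1, 13, and 22) will be provided". The other names the samples that feed the estimation, where that is feasible: "Blood samples for PK collected after the infusion on Day 1, Day 13 or Day 22 prior to the next infusion will be used to" (cut short here). Clearance has a single definition for all of these days: "Systemic clearance after intravenous dosing (L/h), calculated as dose divided by" AUC(0-inf). Vss is the mean residence time to infinity multiplied by that clearance. The data requirement is "A minimum of 3 quantifiable concentration-time data points will be required for calculation of PK parameters".

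The SAP's own sampling schedule (14.3, footnote i) has a fourth full profile: "Day 50: Within 2 hours prior to start of study treatment, at 15 (±5) minutes", then 2, 4, 24, 72 and 120 hours, followed by a Day 56 sample. SAP 3.1.3.2 and Protocol 8.4.2.3 name clearance, peak, volume and trough at steady state as PK outcomes.

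SAP 1 says that content made obsolete by termination is marked as not applicable. Section 9 carries no such mark. It was edited for the termination, since 9.1 drops the population PK analysis for that reason, so the parameter listing in 9.2 is still to be produced.

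**The concern.** Dose over AUC(0-inf) gives clearance after a single dose, because the whole area then comes from that dose. On Day 13 (seventh infusion) and Day 22 (ninth) the curve starts from drug left by earlier infusions. Extrapolating it to infinity credits all of that drug to the current dose. The area is too large and the clearance too small. A reader comparing Days 1, 13 and 22 in the listing could take the fall for a real change in elimination. That matters in a disease where loss of A1PI through the gut is part of the rationale.

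Separately, the profile after the sixth and last weekly infusion is the one best placed to give steady-state values, and no parameters are planned for it.

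**Working it through.** The plan gives no PK figure to reproduce, so this is a check of the formula followed by a count of samples.

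**Inputs**
- Doses (SAP 2 and 14.2): 90 mg/kg on Day 1; 30 mg/kg on Days 3, 5, 7, 9, 11 and 13; 120 mg/kg on Days 15, 22, 28, 36, 43 and 50.
- Half-life: the documents give no human value. Protocol 6.4.1 gives 68.13 h in rabbits. I take 68 to 120 h as an assumption; the upper end is not from the documents.
- Model assumption: one compartment, instantaneous input, endogenous A1PI ignored.

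**Step 1. Bias of the stated formula.** Let A be the amount present just after the dose D (mg/kg), summed over all doses: A = Σ Dᵢ × 2^(−elapsed time/half-life). From that moment AUC(0-inf) = A/CL. The SAP value is D/(A/CL) = CL × D/A, so clearance is understated by the factor A/D.

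Day 13 (D = 30), contributions from Days 1, 3, 5, 7, 9, 11 and 13:
- 68 h: 4.78 + 2.60 + 4.24 + 6.91 + 11.28 + 18.39 + 30 = 78.2; 78.2/30 = 2.61.
- 120 h: 17.05 + 7.50 + 9.90 + 13.06 + 17.23 + 22.74 + 30 = 117.5; 117.5/30 = 3.92.

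Day 22 (D = 120), contributions from Days 1–13 together, Day 15 and Day 22:
- 68 h: 8.65 + 21.65 + 120 = 150.3; 150.3/120 = 1.25.
- 120 h: 33.74 + 45.47 + 120 = 199.2; 199.2/120 = 1.66.

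**Step 2. Area within the interval instead.** Up to the next infusion after τ hours, the area is (A/CL) × (1 − 2^(−τ/half-life)). The estimate relative to true clearance is D/[A × (1 − 2^(−τ/half-life))].
- Day 13 to the Day 15 pre-dose sample, τ = 48: 30/(78.2 × 0.387) = 0.99 at 68 h; 30/(117.5 × 0.242) = 1.055 at 120 h.
- Day 22 to the Day 28 pre-dose sample, τ = 144: 120/(150.3 × 0.770) = 1.04 at 68 h; 120/(199.2 × 0.565) = 1.07 at 120 h.

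| Day | Understatement, dose/AUC(0-inf) | Dose/interval area, relative to true CL |
|---|---|---|
| 13 | 2.6 to 3.9 fold | 0.99 to 1.055 |
| 22 | 1.25 to 1.66 fold | 1.04 to 1.07 |

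**Step 3. Vss.** In this model the curve after any dose is still a single exponential, so the mean residence time to infinity is unchanged. Vss is then understated by the same factor as clearance.

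**Step 4. Day 50.** Days 1, 13, 22 and 50 each have six scheduled post-infusion samples plus one at the next infusion or visit: seven points each, against a minimum of three. By superposition of the same doses over assumed half-lives of 48 to 240 h, the pre-dose trough is 86% to 115% of its weekly steady-state value on Day 22 and 97% to 100% on Day 50.

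Day 56 is 144 h after Day 50 and no infusion is given then. At 68 and 120 h, A on Day 50 is 146.3 and 192.5:
- Area to 144 h: 120/(146.3 × 0.770) = 1.07 and 120/(192.5 × 0.565) = 1.10.
- Area extended to 168 h: 120/(146.3 × 0.820) = 1.00 and 120/(192.5 × 0.621) = 1.00.

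**The case against.** **The size is soft.** The lower half-life is from rabbits and the upper one is assumed. These subjects also have endogenous A1PI, which 9.2 does not subtract. This stands as a limit on the figures. It does not change the direction: with any carry-over A exceeds D. Endogenous protein would remain in an interval-based area too, so the corrected clearance is still approximate.

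**Leaving out Day 50 may be deliberate.** The SAP is dated 13 September 2017, after the termination of 2 June 2017, and both sentences in 9.2 name the same three days. The documents do not say whether the subject reached Day 50. This also stands, but 9.2 gives no reason, whereas 9.1 does give one for dropping population PK.

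**The data are not lost.** A reader might infer that Day 50 samples would go unused. SAP 9.1 lists concentrations without limiting the days, and 9.2 allows additional parameters where appropriate. Only derived Day 50 parameters are not expressly planned.

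**Amendment 1.** A reader might infer that no weekly-dose parameters could be derived, because the amended protocol cuts the earlier weekly profile ("Day 21: Within 2 hours prior to start of study treatment infusion, and at 15" minutes) and keeps the later one ("Day 49: Within 2 hours prior to start of study treatment, at 15" minutes and onward). The documents do not support that for this SAP. SAP 1 and 5.3 state that it follows the original protocol, that Amendment 1 could not be implemented, and that the only subject was treated under the original protocol. In SAP 14.3 Day 22 is a full weekly profile.

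**Conclusion.** The clearance rule in SAP 9.2 is wrong as written for Days 13 and 22, and Vss inherits the error. The direction follows from the formula alone. The factors of about 2.6 to 3.9 (Day 13) and 1.25 to 1.66 (Day 22) are illustrative and rest on one compartment, a half-life of 68 to 120 h and no endogenous A1PI.

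The Day 50 omission is a mismatch between 9.2 and 14.3. That Day 50 is closest to weekly steady state is an inference from the dosing sequence, not a statement in the documents, and Day 22 may not be far from it.

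Severity is minor: the output is a listing for one subject, with no summary, test or decision resting on it.

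**What to change.** In SAP 9.2:
- Keep dose/AUC(0-inf) for Day 1 only.
- On repeat-dose days, compute clearance as dose over the area within the actual dosing interval: Day 13 to the Day 15 pre-dose sample, and Day 22 to the Day 28 pre-dose sample. AUC(0-t) is already among the listed parameters, so this needs only a definition of t.
- Base Vss on the corrected clearance with a mean residence time suited to repeat dosing, or do not report it on those days.
- Add Day 50 to both sentences, using samples through Day 56 and keeping the existing qualifier for cases where estimation is not possible. State whether the area stops at Day 56 (144 h) or is extended to 168 h.

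The cost is a change of wording and one more set of parameters from samples already scheduled. The Day 50 row is empty if the subject did not get that far. Interval-based clearance remains approximate before steady state, within about 7% on Days 13 and 22 under the assumptions above.

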3.1.3.2 Pharmacokinetics

The following noncompartmental analysis PK parameters by day and/or dosing frequency, as applicable, will be assessed:

1. Area under the plasma concentration curve (AUC) from time zero to the last quantifiable activity
2. AUC from time zero to time “t”
3. Systemic clearance at steady state
4. Maximum plasma concentration at steady state
5. AUC from time zero to infinity
6. Apparent volume of distribution at steady state
7. The terminal half-life
8. Mean residence time
9. Trough plasma A1PI levels at steady state

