- ^d Clinical chemistry assessments include: sodium, potassium, chloride, bicarbonate, total protein, albumin, alanine aminotransferase, aspartate aminotransferase, total bilirubin, alkaline phosphatase, blood urea nitrogen, creatinine and glucose.
- ^e Lipid panel includes total cholesterol, very low density lipoprotein, low density lipoprotein, high density lipoprotein and triglycerides.
- ^f Coagulation panel includes fibrin, fibrin split products, fibrinogen and D-dimer.
- ^g Urinalysis assessments include: color, specific gravity, pH, protein, glucose, ketones, bilirubin, urobilinogen, blood, nitrate, leukocyte esterase and microscopic examination (RBC, WBC, bacteria and casts).
- ^h For the determination of stool A₁PI level and clearance and calprotectin concentrations. One sample will be collected either during screening or prior to the first study treatment administration on Day 1. On Days 1 and 13, a sample will be collected during the 24 hours after the start of study treatment infusion. On Day 28, the sample will be collected prior to the start of study treatment infusion.
- ⁱ If study treatment is administered peripherally, the PK samples should be taken from the opposite arm as the study treatment administration, if possible. If study treatment is administered via a central indwelling catheter, the PK samples may be taken from the same infusion line, if the infusion line is flushed prior to collection of the PK sample and the first 3 mL of blood is discarded.
The PK samples for the measurement of plasma A₁PI levels will be collected at the following timepoints:
Part 1, Cohort 1
 - Day 1: Prior to start of study treatment infusion, at 15 (±5) minutes, 2 hours (±12 minutes), 4 hours (±24 minutes), 8 hours (±48 minutes), 12 hours (±72 minutes) and 24 hours (±144 minutes) (ie, Day 2) following the end of study treatment infusion
 - Day 3: Within 2 hours prior to start of study treatment infusion, and at 15 (±5) minutes following the end of study treatment infusion
 - Day 13: Within 2 hours prior to start of study treatment infusion, at 15 (±5) minutes, 2 hours (±12 minutes), 4 hours (±24 minutes), 8 hours (±48 minutes), 12 hours (±72 minutes) and 24 hours (±144 minutes) (ie, Day 14) following the end of study treatment infusion
 - Day 15: Within 2 hours prior to start of study treatment infusion, and at 15 (±5) minutes following the end of study treatment infusion

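### SAP 9.2 lists clearance as dose/AUC(0-inf) after repeated infusions, which biases it low on Days 13 and 22; separately, values labelled as GLASSIA are uncorrected total A1PI

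*SAP*

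**What the plan says.** SAP 9.2 commits to an output: "A listing of PK parameters by Day (Days 1, 13, and 22) will be provided". The data are "Blood samples for PK collected after the infusion on Day 1, Day 13 or Day 22 prior to the next infusion", and the "PK parameters will be estimated for GLASSIA in plasma by non-compartmental methods". AUC(0-inf) runs from predose and is extrapolated with the last concentration over the terminal rate constant; no residual from earlier doses is removed. Clearance is "Systemic clearance after intravenous dosing (L/h), calculated as dose divided by" AUC(0-inf), whatever the day, and Vss is MRTinf multiplied by CL. AUC(0-t) is defined, but clearance does not use it.

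SAP 3.1.3.2 names the outcome as "Systemic clearance at steady state". SAP 14.3 describes "The PK samples for the measurement of plasma" A1PI, so the analyte is the protein itself. Protocol 6.1.1 says that A1PI is made mainly in the liver and circulates, and Protocol 6.4.1 reports that patients with GI GvHD lose their own A1PI in stool.

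Most analysis sections of the SAP carry a statement that derivations and summaries no longer apply. Section 9 does not, and SAP 5.3 allows exceptions to its listings-of-raw-values rule. I therefore read the PK parameter listing as still to be produced.

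**The concern.** Dose/AUC(0-inf) equals clearance only when the whole area comes from the dose in the numerator. That is so after the first infusion. On Days 13 and 22 the area also holds drug from six and eight earlier infusions, while the numerator is one dose. The listed CL is then too low and is not the steady-state clearance named as the outcome. A subject with constant clearance would appear to have different clearances on the three days.

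The second issue is independent of the first. A1PI is endogenous, no assay that separates infused from native protein is described, and 9.2 subtracts nothing. Native A1PI enlarges AUC(0-inf) on every listed day, Day 1 included, so a value labelled as GLASSIA clearance is lower than the same data would give without it.

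**Working it through.** The documents state no CL or bias figure to reproduce, so this is superposition of the SAP schedule.

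**Inputs.** SAP section 2 (original-protocol day numbering): 90 mg/kg on Day 1; 30 mg/kg on Days 3, 5, 7, 9, 11 and 13; 120 mg/kg on Days 15 and 22. Elapsed time is 288 h at the Day 13 infusion and 504 h at Day 22. Half-life h is assumed, because no human value is given; the rabbit terminal value in Protocol 6.4.1 is 68.13 h.

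**Formula (one compartment, bolus).** The residual just before the listed infusion is R = Σ Dᵢ × 2^(−elapsed/h). AUC(0-inf) from that infusion is (D + R)/CL, so listed/true CL = D/(D + R). MRT is unchanged, so Vss has the same ratio.

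**At 68.13 h.**
- Day 13: R = 4.81 + 2.61 + 4.25 + 6.93 + 11.30 + 18.41 = 48.31 mg/kg; ratio 30/78.31 = 0.38.
- Day 22: R = 30.42 mg/kg, of which 21.72 is from Day 15; ratio 120/150.42 = 0.80.

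| Assumed half-life (h) | Day 13 CL/true | Day 22 CL/true |
|---|---|---|
| 24 | 0.75 | 0.99 |
| 36 | 0.60 | 0.96 |
| 68.13 | 0.38 | 0.80 |
| 96 | 0.30 | 0.68 |
| 120 | 0.26 | 0.60 |
| 144 | 0.23 | 0.55 |

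The SAP's own noncompartmental method was also run at its sampling times in one- and two-compartment models (terminal half-life 48 to 120 h, 1-h infusion, fast phase of 16.3 h carrying 0 to 70% of AUC, no endogenous A1PI). CL was 0.25 to 0.78 of true on Day 13 and 0.60 to 0.97 on Day 22; Vss was 0.26 to 0.66 and 0.60 to 0.95. Both were low in every case.

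**Interval clearance.** Dose/AUC(0-tau) relative to true is D/[(D + R)(1 − 2^(−tau/h))]. At 68.13 h:
- Day 13, tau = 48 h: 30/(78.31 × 0.386) = 0.99.
- Day 22, tau = 144 h: 120/(150.42 × 0.769) = 1.04.

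Over 36 to 144 h the ranges are 0.99 to 1.11 and 1.02 to 1.09.

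**Endogenous A1PI.** Assume 0.5 to 1.5 mg/mL and a volume of 60 mL/kg. The 90 mg/kg dose raises the level by 90/60 = 1.5 mg/mL, so the assumed background is one third to all of that rise. With the SAP method on Day 1, CL is 0.18 to 0.54 of true in one compartment (36 to 144 h). Two-compartment cases widen this to about 0.14 to 0.85. With endogenous A1PI added, Day 22 Vss exceeded true in 4 of 48 cases (up to 1.42).

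**The case against.** The SAP does not bar a steady-state clearance. Section 9.2 permits further parameters where suitable, 9.1 provides case-by-case review of partial data, and AUC(0-t) is already defined. This stands as far as it goes: the plan permits CLss. But it does not specify it, and the stated formula for the listed CL is unchanged. The case-by-case review concerns whether the data suffice, not which formula applies.

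SAP section 1 says that only listings of raw values will be produced, which could suggest that no parameters will be derived. Section 9.2 is more specific and is not marked as inapplicable, so I read the listing as live, but the tension is real.

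The analyte issue is largely one of labelling: SAP 14.3 and the trough item in 3.1.3.2 already name A1PI. That is fair, and it is why the remedy is mainly a label.

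Three stronger readings are not supported:
- A reader might infer that listed Vss must be low. Carry-over alone lowered it in the cases run, but endogenous A1PI can reverse the net direction on Day 22.
- A reader might infer that half-life and MRT are distorted in a known direction. Carry-over alone leaves them unchanged in one compartment. Endogenous A1PI pushes them up, but sampling that ends at 48 h on Days 1 and 13 can push them down.
- A reader might blame the rule that "predose samples that are BLQ or missing will be assigned a numerical value of zero". Its effect on Day 13 CL is about 0.4% with a 1-h infusion and 1.0% with a 3-h infusion (68 h, one compartment). Setting the value to missing would leave an AUC that starts at predose without a starting point.

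**Conclusion.** The concern holds as a minor error of specification. The downward carry-over bias in CL follows from the formula, because any positive residual enlarges AUC(0-inf), and it appeared in every carry-over case run. Its size rests on an assumed half-life: it is large on Day 13 and moderate on Day 22, and at 24 h it almost vanishes on Day 22 (0.99 to 1.00) while Day 13 is still about 0.75. The net direction of Vss on Day 22 is not certain. The endogenous effect lowers CL on all days relative to the same data without it, but it cannot be sized from the documents.

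A reader might infer that the trial's PK conclusions are compromised. The documents do not support that. One subject was enrolled, the study was terminated, and no test, summary or Part 2 decision uses this listing. The documents do not say whether Day 13 or Day 22 samples exist. Concentrations and times are listed under SAP 9.1, so CLss could be recomputed.

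**What to change.** On Days 13 and 22, list CLss = dose/AUC(0-tau). Set tau = 48 h on Day 13. State tau for Day 22: the SAP schedule has the sample for "Day 28: During the Day 28 clinic visit, but must be prior to the next study treatment", which is 144 h after Day 22 against a nominal weekly 168 h. Note that Day 22 is only near steady state.

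Keep dose/AUC(0-inf) and the derived Vss for Day 1 only. Read them with the extrapolated percentage of AUC that 9.2 already lists, because sampling ends at 48 h and may miss the terminal phase.

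Label every uncorrected parameter as total A1PI. The interval formula removes carry-over, not the endogenous part. Values with the Day 1 predose level subtracted may be added, but only as a supplement, because endogenous A1PI may drift as stool losses change. If it rises by 0.25 mg/mL after Day 1, subtracted CLss on Day 13 is 0.65 to 0.98 of true; if it falls by that amount, 1.23 to 2.13 (60 mL/kg assumed, one- and two-phase models).

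The cost is SAP wording and a small change to the PK code for one listing. All samples needed are already scheduled.
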